### **2.2.3 Sample Size Justification**

The objective of this safety pilot study is to determine if lyophilized lucinactant administration is safe and tolerable, and to assess the impact on oxygenation for those patients suffering with COVID-19. As a result, no formal sample size calculation was performed. A total of 20 subjects should be sufficient to provide evidence that liquid lucinactant can be safely delivered as an intratracheal bolus.

Thus, 20 subjects (out of approximately 60 screened) will be enrolled.

## 2.2.4 Study Schedule

Measurement/Procedure	Primary Phase Through Day 30			
	Screening	Treatment Period (Day 1)	Post-Treatment Period (Days 2-5)	Final Period (Days 6 to 30)
Informed consent	X			
Inclusion/exclusion Criteria	X			
Demographics	X			
Medical history	X			
Physical examination	X			
Enrollment		X		
Study treatment administration		X		
Vital signs	X	X	X 	X
ABG (PaO 2 , PaCO 2 , pH)		X 	X	X
FiO 2 , SpO 2 , P aw , EtCO 2		X 	X	X
Ventilator parameters (rate, peak and plateau pressure, lung compliance)		X 	X 	
Respiratory support parameters	X	X	X	X
Pressure volume loops		X 		
AEs/SAEs		X	X	X
Concomitant medications	X	X	X	X
Final Visit/Discharge				X 

Note: Day 1 for all subjects is the day of enrollment.

 Time 0 (study treatment), 1, 2, 4, 8, 12, 18, 24 hours after treatment

 Recorded every 12 hours at 08:00 and 20:00 through Day 5.

 Recorded every 2 hours through 24 hours.

 Occurs at Day 30, withdrawal from the study, or death (whichever occurs first).

### **3 STUDY SUBJECT CHARACTERISTICS**

#### **3.1 Subject Disposition**

Subject disposition will be summarized by treatment group using frequency and percent. The number of subjects screened, randomized and received study medication (modified intent-to-treat [mITT] population), received study medication regardless of randomization (safety population), and without protocol violations (per-protocol population) will be described. If more than 5% of subjects experience a treatment interruption, a population of subjects without interruptions will also be defined.

The number of subjects who completed the study or died will be summarized using frequency and percent by treatment group and overall. Reasons for early discontinuation from the study include withdrawal of consent and lost-to-follow up. A subject may withdraw consent (through their legally authorized guardian) at any time without prejudice to further care.

The number of subjects who discontinued treatment early will be summarized using frequency and percent by treatment group and overall. Reasons for early discontinuation of treatment include device failure or malfunction, AE or ADE during dosing, PI's best medical judgment, and respiratory deterioration during dosing.

#### **3.2 Demographics and Baseline Characteristics**

##### **3.2.1 Demographics**

Demographic parameters will be summarized by treatment group and assessed qualitatively for homogeneity of treatment groups. Continuous variables (eg, age, weight) will be summarized using mean, standard deviation (SD), median, minimum, and maximum. Categorical variables (eg, sex, race, ethnicity) will be summarized by treatment group using frequency and percent.

Race categories with small numbers (frequencies of percentages of < 10%) will be combined as 'Other' for summary displays.

##### **3.2.2 Medical History**

Medical history findings will be documented during screening. And incidence of medical history findings will be summarized by treatment group using frequency and percent.

### **3.3 Study and Concomitant Medication**

#### **3.3.1 Compliance**

Study treatments will be administered in an in-patient setting (ie, ICU) by the PI or a person approved for dosing by Windtree. Completion of drug delivery for each treatment and re-treatment will be monitored; no other compliance measurements will be employed.

Percent compliance for this study is not applicable as all subjects will be administered at least one dose by study staff in the NICU. The number of subjects who experienced treatment interruptions for the initial or repeat doses will be summarized by treatment group.

Lung compliance should be recorded during screening and lung compliance will be summarized as change from baseline at each time point measured using mean, SD, median, minimum, and maximum.

#### **3.3.2 Number of Doses**

The number of doses (initial and repeat study treatments) received by subjects and the number of times a subject qualified for a repeat dose will be summarized by treatment group.

#### **3.3.3 Concomitant Medication**

Concomitant medications and therapies required for the general care of the subject are permitted, including remdesivir and off-label drugs. Other investigational agents or investigational medical devices should be avoided. Concomitant medications will be documented until the time the subject completes the Day 30, is discharged from the hospital, dies, or is transferred to another hospital. Dose, route, unit, frequency of administration, indication for administration, and dates of medication will be captured on the CRF.

Concomitant medications will be classified according to the World Health Organization (WHO) drug dictionary (March 2020 or later). Applicable concomitant medications (sedatives, paralytics, vasopressors, anti-coagulants, COVID-directed antiviral and anti-inflammatory therapy) will be recorded from enrollment until the final subject assessment. Medications will be summarized using frequency and percentages for each treatment group by drug category and generic name.

### **3.4 Protocol Violations/Deviations**

A protocol violation occurs when the PI fails to adhere to any significant protocol requirement affecting the inclusion, exclusion, subject safety, and primary endpoint criteria. A protocol deviation is any deviation from the protocol that does not rise to the level of a protocol violation. All protocol violations/deviations will be summarized by treatment group and listed by subject. Subjects with protocol violations will not be included in the per-protocol population.

## **4 EFFICACY ANALYSIS**

The efficacy objective is to evaluate the safety and feasibility of lucinactant SRT in treating COVID-19, as assessed by OI (defined as  $P_{aw} \times FiO_2 \times 100 / PaO_2$ ) at 12 hours post dosing and other physiological and outcome measurements through 24 hours or through Day 30. In addition, the study will assess other measurements changing from the baseline and the ability to administer up to 3 lucinactant for inhalation repeat treatments.

### **4.1 Efficacy Populations**

For efficacy analyses, subjects will be summarized according to their randomized treatment.

The statistical analysis of both the primary and secondary objectives will be based on all enrolled subjects. For the efficacy analysis, the primary analysis will be based on a modified intent-to-treat population (mITT). In addition, populations of all randomized subjects (ITT) and subjects with no major protocol deviations (per-protocol) will be evaluated based upon the treatment group to which they were randomized. If treatment interruptions are experienced by > 10% of subjects, a population of subjects without treatment interruptions will also be defined and analyzed.

#### **4.1.1 Modified Intent-to-Treat Population**

The modified intent-to-treat (mITT) population is the primary efficacy analysis population and is defined as all enrolled subjects who received any treatment.

#### **4.1.2 ITT Population**

The ITT population is defined as all subjects who were randomized in the study, regardless of receipt of study treatment.

### **4.2 Statistical Analysis**

All analyses will be performed for all subjects combined and by treatment group, by baseline value, as appropriate.

All efficacy and safety parameters will be evaluated using summary statistics. For continuous (parametric) data, data will be summarized using number (n), mean, standard deviation (SD), median, 1st quartile, 3rd quartile, minimum, and maximum. For categorical (discrete) data (eg, sex, race), data will be summarized using frequency (n) and percent.

See Section 7, Statistical Technical Issues, for details on statistical methods and calculations.

#### **4.2.1 Primary Efficacy Endpoint**

The primary endpoint is the change from baseline in OI through 12 hours post dosing. OI is defined as  $(\text{FiO}_2 \times P_{\text{aw}} \times 100) / \text{PaO}_2$ . OI will be summarized using mean, standard deviation (SD), median, minimum, and maximum.

#### **4.2.2 Secondary Endpoints**

The secondary efficacy is to assess other physiological and outcome measurements through 24 hours or through Day 30 to ensure consistency of results across multiple endpoints.

Through 24 hours post treatment, OI,  $\text{FiO}_2$ ,  $\text{PaO}_2$ ,  $\text{SpO}_2$ ,  $\text{PaCO}_2$ , P/F and S/F ratios, change in plateau pressure and PIP measured on the ventilator, VI, and lung compliance will be summarized as change from baseline at each time point measured using mean, SD, median, minimum, and maximum.

Through 30 days post treatment, Daily lung compliance on ventilator, ventilator free days, days in the ICU, days in the hospital, organ failure free days, and all-cause mortality will be summarized as was done for the primary endpoint.

All deaths will be summarized using frequency and percent, overall and by type of death (respiratory or not respiratory) and included as part of the assessment of safety. Time to death will also be summarized using mean, standard deviation (SD), median, minimum, and maximum. Also, the deaths will be listed by subject and narratives for each death will be included. In this study, the secondary endpoint of ventilator-free days (VFD) is a mortality adjusted assessment. This issue will be dealt with in more detail in preparation for the next study.

#### **4.3 Missing Data**

Missing values represent a potential source of bias in a clinical trial. Hence, every effort will be undertaken to fulfill all the requirements of the protocol concerning the collection and management of data; however, some missing data is inevitable. No imputation, including last observation carried forward, will be done for the any parameters; only available data will be considered. Any missing data or data anomalies will be communicated to the site(s) for clarification/resolution.

#### **4.4 Subgroup Analyses**

Not applicable. No sub-group analyses are planned in this study.

#### **4.5 Exploratory Analyses**

Exploratory analyses may be performed based upon subject responses to treatment.

## **5 SAFETY ANALYSES**

### **5.1 Safety Population**

Since this is an open-label study with only one treatment group. The safety population is defined as all subjects who received any study medication. All safety assessments will be based on this population.

Safety analyses will be summarized by all subjects combined.

### **5.2 Extent of Exposure**

This is a multicenter, single-treatment study. All subjects will be enrolled into the lucinactant treatment group if they meet all the screening criteria. Enrolled subjects will receive reconstituted lyophilized lucinactant (30 mg total TPL/mL) as a liquid at 160 ml (~80 mg TPL/kg lean body weight) in the first dose. The number of subjects who receive a repeat dose, the number of doses received, the amount of treatment received (based on number of treatment), and the number of subjects whose study treatment is terminated early will be summarized.

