For the efficacy analysis, populations of all enrolled subjects who received any treatment (modified intent-to-treat [mITT]) will be evaluated. For the safety analysis, all enrolled subjects who received any lucinactant (including partial doses) will be evaluated.

All efficacy and safety parameters will be evaluated using summary statistics. For continuous variables, n, mean, standard deviation, median, min, and max will be presented; for discrete variables, frequency and percent will be presented.

All deaths will be summarized using frequency and percent, overall and by type of death (respiratory or not respiratory) and included as part of the assessment of safety. Also, the deaths will be listed by subject and narratives for each death will be included.

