Venticute® (50 mg PL/ml) was administered to adult ARDS patients by endotracheal instillation (41). Up to 4 doses of 50 mg/kg (1 ml/kg) were administered to patients. Overall survival at 28 days after treatment was 66% and the median number of ventilator-free days was 0. There was no significant difference in mortality or the need for mechanical ventilation between the Venticute and control groups. Patients receiving Venticute had significantly greater, improvement in blood oxygenation during the initial 24 hours of treatment than patients receiving standard of care. However, this improvement was not sustained and was not significantly different by 48 hours. These observations suggest the possible need for a prolonged treatment period, possibly with greater intervals between doses, with a larger number of doses, or with a larger dose volume. Up to 3 treatments (dose = 30 mg [60 mg PL/ml] per centimeter of height) were allowed if retreatment criteria were met. Infasurf administration was not associated with improved survival, length of stay or oxygenation. The authors speculated that the lack of response could be related to insufficient dosing of surfactant, since they choose not to administer a second dose of surfactant if the first was without clear benefit. They also concluded that the lack of oxygenation benefit may

be due to ineffective timing of instillation and/or administration technique rather than lack of efficacy of exogenous surfactant (40).

Based on previous clinical studies, as well as studies in several animal models of ARDS, the proposed dose of lucinactant (30 mg total PL/ml) is 160 ml (80 mg/kg lbw, based on an estimated 60 kg lbw patient similar to those enrolled in the Survanta and Venticute studies). Windtree believes that this dose addresses both the amount of PL required to sufficiently restore alveolar surface tension and the volume of lucinactant required to adequately coat the alveolar surface.

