6.1.2 Dosing and Administration

Eligible patients will be enrolled into the study and receive lucinactant treatment. Treatment initiation is to begin within 6 hours of enrollment. The time of enrollment is defined as the time at which it has been confirmed that the subject has met all inclusion criteria and has not met any exclusion criteria, and a request to the pharmacy to prepare study drug has been made. Enrollment should occur within 7 days of endotracheal intubation and MV.

Initial Dose

Reconstituted lyophilized lucinactant is administered using the following instillation procedure:

- a. The ventilator will be set at an FiO₂ of 1.00.
- b. To prevent cough and throat closure, the patient may receive a short-acting paralytic.
- c. Lucinactant will be administered via a number 10 French end-hole suction catheter positioned in the trachea at the end of the endotracheal tube. The suction catheter will be inserted into the ventilator's inspiratory tubing via a side-port connector.
- d. The total dose of lucinactant will be divided into four quarter-doses (40 ml). Each quarter-dose will be further sub-divided into aliquots of 20 ml. Each quarter-dose will be instilled in one of the four positions listed below, one aliquot at a time. After each quarter dose, ensure the patient is stable before continuing the dosing.

- 1. Quarter-dose administered with the patient supine and positioned 45° to the right. Each aliquot will be followed by 1 minute of ventilation.
- 2. Quarter-dose administered with the patient supine and positioned 45° to the left. Each aliquot will be followed by 1 minute of ventilation.
- 3. Quarter-dose administered with the patient supine and positioned 45° to the right. Each aliquot will be followed by 1 minute of ventilation.
- 4. Quarter-dose administered with the patient supine and positioned 45° to the left. Each aliquot will be followed by 1 minute of ventilation.

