During the administration of the lucinactant, the investigator should monitor the patient's oxygen saturation by pulse-oximetry. If the subject does not tolerate one of the 40 ml quarter doses, the dosing for that dose may be terminated at that time. It is recommended that the other quarter doses remain 40 ml; however, a lower dose may be administered for the remaining aliquots at the Investigator's discretion. The investigator will remain with the patient during the first 10 minutes post-treatment. No ventilator changes are to be made during this 10-minute period unless cyanosis or bradycardia occur. At the end of this 10-minute period, the patient's FiO₂ should be weaned to the patient's pre-treatment FiO₂. The patient should not be suctioned for one hour following dosing.

If, in the opinion of the investigator, the patient experiences clinically significant desaturations, hypoxia and/or bradycardia, the lucinactant administration should be temporally suspended to allow the patient to recovery. If the patient doesn't not recovery in a reasonable time, the administration should be terminated. If the administration procedure is re-started and the patient experiences a second episode of clinically significant desaturation, hypoxia and/or bradycardia, the lucinactant administration should be immediately terminated.

Retreatment Doses

Up to 3 retreatment doses are allowed no sooner than 6 hours apart (from completion of previous dose). Subjects are eligible for retreatments if they remain on MV, there is no evidence of pneumothorax, the P/F ratio is under 300 (or S/F ratio is under 315 (43), if no arterial line is present), and there are no safety concerns that would prevent retreatment (in the opinion of the investigator). Retreatments are given at the discretion of the investigator, but it is encouraged that retreatments be given at the recommended time interval if the patient is still receiving MV and meets all retreatment criteria.

Retreatment should be performed in the same manner as the initial treatment.

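### SAP 5.2 bases the amount of drug received on the number of treatments, so the exposure summary cannot show the volume delivered when a dose is cut short or reduced

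*SAP*

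**What the plan says.** SAP 5.2 (Extent of Exposure) describes the initial treatment as "lyophilized lucinactant (30 mg total TPL/mL) as a liquid at 160 ml (~80 mg TPL/kg lean body weight) in the first dose". It then lists what will be summarised: subjects with a repeat dose, the number of doses, "the amount of treatment received (based on number of treatment"), and subjects whose treatment ended early. In the SAP's list of tables, Table 3.2 covers how many treatments were given and when. No table or text section calls for millilitres or milligrams delivered.

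Protocol 6.1.2 shows that one treatment is not a fixed quantity. "The total dose of lucinactant will be divided into four quarter-doses (40 ml" each), and every quarter-dose is given as 20 ml aliquots. Then: "If the subject does not tolerate one of the 40 ml quarter doses, the dosing for that dose may be terminated at that time". The same paragraph recommends keeping the other quarter-doses at 40 ml, but adds that "a lower dose may be administered for the remaining aliquots" at the investigator's discretion. After a second clinically significant desaturation, hypoxia or bradycardia episode, "the lucinactant administration should be immediately terminated". SAP 2.2.1 repeats the provisions on stopping a quarter-dose and reducing the rest.

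Subjects with incomplete doses stay in the analysis. For safety, the Protocol 1.1 Summary says that "all enrolled subjects who received any lucinactant (including partial doses) will be evaluated". For efficacy, SAP 4.1.1 places anyone who received any treatment in the mITT population.

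**The concern.** A count of treatments measures amount only if every treatment delivers the same quantity. Here one treatment can be anything from a single 20 ml aliquot to the full 160 ml. Since 160 ml is the full dose, crediting it to each treatment can overstate the amount but never understate it. The error falls on subjects who did not tolerate dosing, the group a tolerability study most needs to describe. A count-based amount also adds nothing to the number of doses listed beside it in SAP 5.2: it is that number times a constant.

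Tolerability of the bolus is a primary endpoint. The dose justification in Protocol 4.3 rests on volume as well as on phospholipid mass: it contrasts earlier studies at 2-4 ml/kg with later ones at about 1 ml/kg that it describes as failing. SAP 1.2 says that the efficacy estimate will be used to size future studies. A reader of the results therefore needs to know how much drug lies behind the tolerability findings and the OI changes.

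**Working it through.** **Inputs.** Full treatment 160 ml at 30 mg TPL/ml (SAP 5.2); four quarter-doses of 40 ml, each in 20 ml aliquots (Protocol 6.1.2); reference patient from Protocol 4.3, "80 mg/kg lbw, based on an estimated 60 kg lbw patient"; one initial treatment and up to three repeats (SAP 2.2.1). The documents give no rate of partial delivery, so the rates in step 4 are assumptions.

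**1. The plan's own figures reproduce.** 4 x 40 = 160 ml. 160 x 30 = 4800 mg. 4800 / 60 = 80 mg/kg. 160 / 60 = 2.67, or about 2.7 ml/kg.

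**2. One incomplete treatment.** Ratio = credited volume / delivered volume = 160 / v.

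| Delivered (ml) | mg TPL (v x 30) | mg/kg at 60 kg | 160 / v |
|---|---|---|---|
| 160 | 4800 | 80 | 1.00 |
| 140 (one quarter-dose stopped after its first aliquot) | 4200 | 70 | 1.14 |
| 120 | 3600 | 60 | 1.33 |
| 80 | 2400 | 40 | 2.00 |
| 40 | 1200 | 20 | 4.00 |
| 20 (one aliquot only) | 600 | 10 | 8.00 |

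**3. Cumulative amount.** Complete treatments dilute the ratio. For example, a subject with four treatments, one of them stopped after 40 ml, is credited with 4 x 160 = 640 ml but received 3 x 160 + 40 = 520 ml. The ratio is 640 / 520 = 1.23.

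**4. Mean volume per treatment.** Let a fraction f of treatments be partial, each missing d ml. True mean = 160 - f x d; overstatement = 160 / (160 - f x d) - 1.

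| Missing per partial treatment | f = 10% | f = 20% | f = 30% |
|---|---|---|---|
| 20 ml | 158 ml, 1.3% | 156 ml, 2.6% | 154 ml, 3.9% |
| 40 ml | 156 ml, 2.6% | 152 ml, 5.3% | 148 ml, 8.1% |
| 120 ml | 148 ml, 8.1% | 136 ml, 17.6% | 124 ml, 29.0% |

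With f = 0 the overstatement is zero.

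**5. What the other planned summaries show.**
- SAP 5.2 and 3.1 count subjects whose treatment ended early; SAP 3.1 also names the reasons.
- SAP 3.3.1 counts subjects with interruptions of initial or repeat doses. It says that completion of delivery is monitored but specifies no summary of completion, and it declares percent compliance not applicable.
- Listing 4.1 describes treatments ended early.
- Protocol 7.1 and 8.3.1.2 have the reason, time and incidence of interruptions and discontinuations recorded.

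The tabulations count subjects or events. Stopping after 20 ml and stopping after 140 ml look the same in them. An aliquot reduced without interruption or termination appears in none of these summaries.

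**6. Does the exposure amount enter any other analysis?** No. AEs are frequencies and percents of subjects (SAP 5.1, 5.3), OI is summarised descriptively (SAP 4.2.1), and SAP 7.3 states that no model is fitted.

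**The case against.** The strongest reply is that the gap is narrow. Three stronger readings are tempting, and the documents support none of them.

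First, a reader might infer that incomplete delivery is hidden. It is not: early terminations, discontinuations and interruptions are all counted, early terminations are listed, and reasons and times are collected. SAP 3.1 and 4.1 even provide for a population without interruptions once a threshold is passed. That stands. What is missing is the volume, and any reduction made without an interruption or termination.

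Second, a reader might infer that AE rates and OI changes would be wrong. They would not: no planned analysis uses the exposure amount, so each of those figures is the same under either definition. That also stands.

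Third, a reader might take a large mean overstatement as established. No sentence says that each treatment is credited at 160 ml; this is the natural reading of a loosely worded parenthesis. The upper range assumes that each partial dose loses 120 of 160 ml, whereas Protocol 6.1.2 recommends keeping the other quarter-doses at 40 ml. The loss of one quarter-dose gives the much smaller 40 ml row.

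Nor can it be said that volume is not collected. Protocol 8.3.1.2 does not name it, but the dosing eCRF and study manual are not among the documents.

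The reply does not remove the point that a count cannot represent an amount when the protocol provides for partial amounts.

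**Conclusion.** The point holds as a wrong derivation of one descriptive exposure measure. If each treatment is credited at its nominal 160 ml, the amount is overstated for every incomplete treatment, from 1.14 times at 140 ml delivered to 8 times at 20 ml, and is exact for complete ones. The effect on the mean depends on rates that the documents do not give. With an assumed 10-30% of doses partial, it is 2.6-8.1% if each misses 40 ml and 8-29% if each misses 120 ml. If all doses are complete it is zero, and the planned summaries of amount cannot show which of these cases occurred.

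The consequence is limited to the exposure summary against which tolerability and OI change are read. No population, sample size, AE figure or OI figure is affected, and nothing here bears on whether the dosing rules themselves are right.

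**What to change.** In SAP 5.2 and Table 3.2, define amount received as the millilitres actually instilled, converted as mg TPL = ml x 30, and summarise it per treatment and cumulatively per subject. Report the number and percent of initial doses and of retreatments delivered in full, and the number that were not, including those with reduced quarter-doses that were never interrupted or stopped. If the eCRF does not already capture delivered volume for each quarter-dose, name it as a collected item.

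The cost is at most one data field per quarter-dose and a changed derivation. If the eCRF already holds the volume, only the derivation and the table change. Reported exposure may come out slightly lower than a count would suggest.
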